4.6.3.2 Presentations

All laboratory data will be presented for the on-treatment and on-study periods using international system of units and presented as detailed in [Table 2](#).

Clinical laboratory parameters will be presented by scheduled visit, separately for haematology and chemistry parameters. All parameters will be presented as continuous variables with descriptive statistics for all visits at which an assessment is scheduled. Observed value, absolute change from baseline will be presented using descriptive statistics for all scheduled assessments after baseline.

The number of participants with treatment-emergent laboratory parameter abnormalities will be presented categorically in frequency tables, according to the categories defined in Section [4.6.3.1](#). Risk differences between active treatment groups and Placebo will be presented with 95% CI.

Key subject information will be separately listed for participants with haematology abnormalities, chemistry abnormalities, or potential Hy's law. Additionally, individual chemistry laboratory measurements and individual haematology laboratory measurements will be listed.

Shift tables from baseline to maximum on-treatment and on-study value, and from baseline to minimum on-treatment and on-study value will be presented by treatment group according to the categories defined in Section [4.6.3.1](#).

A descriptive table for maximum ALT and AST versus maximum total bilirubin for the on-treatment and on-study analysis periods will be shown.

Out-of-range values for safety laboratory will be flagged in individual listings as well as summarized descriptively.

4.6.4 Clinical Laboratory, Urinalysis

4.6.4.1 Definitions and Derivations

Urinalysis will be done according to the schedule of activities in the CSP (Table 1). The parameters included in the scope of the analysis are specified in the list below:

Table 10 – Renal Safety Variables

Qualitative	Quantitative

• Urobilinogen• Erythrocytes• Glucose	
• pH• Specific gravity• Albumin/Creatinine (ratio)

• Ketones• Leukocytes esterase• Nitrites• Protein	
--	--

Abnormalities in Urinalysis Parameters

Treatment emergent abnormalities are defined as abnormalities that manifested after the first administration of study treatment.

For quantitative parameters, participants with treatment emergent urinalysis abnormalities will be categorized according to mutually exclusive thresholds based on central laboratory ranges: < LLN, > ULN.

In addition, abnormalities in 'albumin/creatinine' (ratio) will be defined as ≥ 300 mg/g.

Shift Tables

Shift tables will be presented for all parameters according to thresholds described below.

For qualitative parameters, the values will be reported using ordered categorical values, where 'Negative' represents the absence of abnormality, and increasing levels (Trace, +, ++, +++, +++) indicate progressively worsening of abnormality.

For quantitative parameters, the categories will be defined according to the mutually exclusive thresholds based on central laboratory ranges (when applicable):

- < LLN
- \geq LLN and \leq ULN
- > ULN

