## 1.2      Schedule of Activities

The Schedule of Activities (SoA) is provided in [Table 1](#).

**Table 1** Schedule of Activities

	Screening	Treatment period							Final follow-up/EDV
Visit number	1	2	3	4	5	6	7	8	
Study day	D -21 to D -1	D1	D8	D15	D29	D57	D85	D99	
Visit window			± 3 days						
Informed consent	X								
Inclusion/exclusion criteria	X	X							
Demographic data	X								
Medical history	X								
Height, weight, and BMI (height at screening only)	X	X	X	X	X	X	X	X	
Drugs of abuse screening a	X								
Urine pregnancy test (local) b	X	X							
FSH	X								
LH	X								
HbA1c	X							X	
Serology	X								
COVID-19 test c	X	X							
Concomitant medication review	X	X	X	X	X	X	X	X	
Dispensing of AZD0780/Placebo (35 tablets per bottle)		X			X	X			
Study intervention administration (AZD0780/Placebo)		X (Once daily oral dosing; Day 1 through Day 84)							

**Table 1** Schedule of Activities

	Screening	Treatment period						Final follow-up/EDV
Visit number	1	2	3	4	5	6	7	8
Study day	D -21 to D -1	D1	D8	D15	D29	D57	D85	D99
Visit window			± 3 days					
Safety and Tolerability								
Adverse event review	X (SAEs only)	X (AEs as of dosing)	X	X	X	X	X	X
Physical examination (full)	X	X						X
Physical examination (brief)			X	X	X	X	X	
Vital signs (BP, pulse and temperature, respiratory rate, pulse oximetry) d	X	X	X	X	X	X	X	X
12-lead safety ECG e	X	X	X	X	X	X	X	X
Clinical safety laboratory evaluations (chemistry, hematology, coagulation, urinalysis)	X	X	X	X	X	X	X	X
Urine renal safety biomarkers: albumin, creatinine, total protein	X	X	X	X	X	X	X	X
Efficacy/Pharmacokinetics/Pharmacodynamics (fasted)f								
Lipid profile (TC, HDL-C, non-HDL-C, triglycerides)	X	X	X	X	X	X	X	X
LDL-C	X	X	X	X	X	X	X	X
ApoB		X	X	X	X	X	X	X

**Table 1** Schedule of Activities

	Screening	Treatment period							Final follow-up/EDV
Visit number	1	2	3	4	5	6	7	8	
Study day	D -21 to D -1	D1	D8	D15	D29	D57	D85	D99	
Visit window			± 3 days						
ApoA1		X			X	X	X	X	
Lp(a)		X			X	X	X	X	
hsCRP		X			X	X	X	X	
PK plasma samples f			X	X	X	X	X		
Exploratory									
Blood sample for total PCSK9		X							
Blood (serum) sample for biomarker analyses		X			X	X	X	X	
Blood (plasma) sample for biomarker analyses		X			X	X	X	X	

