**Table 6** **Laboratory Safety Variables**

Hematology/Hemostasis/Glycaemic control
 
 
• Blood 
 
○ Hematocrit
 
○ Hb
 
○ Leukocyte count
 
○ Leukocyte differential count (absolute count)
 
○ MCV
 
○ MCH
 
○ MCHC
 
○ Platelet count
 
○ RBC
 
○ Reticulocyte absolute count
 
○ Coagulation
 
○ HbA1C
 
 
 
 
Urinalysis
 
 
• Microscopy including white blood cell/RBC and casts
 
• Urine 
 
○ Appearance and color
 
○ Urobilinogen
 
○ Blood
 
○ Glucose
 
○ Ketones
 
○ Leukocytes
 
○ Nitrites
 
○ pH
 
○ Protein
 
○ Specific gravity
 
 
 
• Urine renal safety biomarkers 
 
○ Albumin
 
○ Creatinine
 
○ eGFR
 
○ Total protein
 
 
 
	
Clinical Chemistry
 
 
• Plasma/Serum 
 
○ Albumin
 
○ ALP
 
○ ALT
 
○ AST
 
○ Bilirubin, total
 
○ Bicarbonate
 
○ Blood urea nitrogen
 
○ Creatinine
 
○ GGT
 
○ High sensitivity CRP
 
○ Potassium
 
○ Sodium
 
○ Total Protein
 
 
 
 
Endocrinology
 
 
• Serum 
 
○ FSH (women only, at screening)
 
○ LH (women only, at screening)
 
 
 
 
Pregnancy Dipstick Test
 
 
• Pregnancy test (urine human chorionic gonadotropin)a
 
 
Viral Serology (screening only)
 
 
• HIV I
 
• HIV II
 
• HBsAg
 
• Hepatitis C virus antibody
 

--	--

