### **8.3.4 AEs Based on Examinations and Tests**

Deterioration as compared to baseline in protocol-mandated laboratory values and vital signs, should only be reported as AEs if they meet any of the following:

- Fulfil any of the SAE criteria
- Are the reason for discontinuation of the IMP
- Are clinically relevant as judged by the investigator (which may include but is not limited to consideration as to whether intervention or non-planned visits were required or other action was taken with the IMP, eg, dose adjustment or drug interruption).

If deterioration in a laboratory value/vital sign is associated with clinical signs and symptoms, the sign or symptom will be reported as an AE and the associated laboratory result/vital sign

will be considered as additional information. Wherever possible the reporting investigator uses the clinical, rather than the laboratory term (eg, anemia vs low hemoglobin value). In the absence of clinical signs or symptoms, clinically relevant deteriorations in non-mandated parameters should be reported as AE(s).

Deterioration of a laboratory value, which is unequivocally due to disease progression, should not be reported as an AE/SAE.

Any new or aggravated clinically relevant abnormal medical finding at a physical examination as compared with the baseline assessment will be reported as an AE unless unequivocally related to the DUS.

The results from the protocol mandated laboratory tests and vital signs will be summarized in the CSR.

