#### **9.4.3 Safety**

Safety data will be summarized descriptively and will not be formally tested.

Safety data will be presented in the data listings.

Adverse events will be summarized by PT and SOC using MedDRA vocabulary.

Furthermore, listings of SAEs and AEs that led to withdrawal will be made and the number of participants who had any AE, SAEs, AEs that led to withdrawal, and AEs with severe intensity will be summarized.

Tabulations and listings of data for vital signs, clinical laboratory tests be presented. Results from safety ECGs will only be listed. Any new or aggravated clinically relevant abnormal

medical physical examination finding compared to the baseline assessment will be reported as an AE.

Out-of-range values for safety laboratory will be flagged in individual listings as well as summarized descriptively.

Safety analyses will be performed using the safety analysis set unless otherwise specified. Details of safety analyses will be provided in the SAP.

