Statistical analysis method for secondary endpoint(s)	11/18/2024	Section 4.2.2.7, 4.2.3.7 and 4.2.2.6: Subgroup analyses repeated using the treatment policy strategy.	Yes	Study team's request.
Statistical analysis method for secondary endpoint(s)	11/18/2024	Section 4.2.3.1: definition updated to clarify the handling of intercurrent events.	Yes	To improve clarity.
Statistical analysis method for secondary endpoint(s)	11/18/2024	Section 4.2.3.7 and 4.2.2.6: Subgroup analyses added based on baseline Lp(a) values.	Yes	Study team's request.
Statistical analysis method for secondary endpoint(s)	11/18/2024	Section 4.2.3.7 and 4.2.2.6: Subgroup analyses repeated on treatment policy strategy.	Yes	Study team's request.
Exposure	11/18/2024	Section 4.6.1: Formula updated based on DA form instead of EXL.	Yes	Study team's decision.
Safety Analysis	11/18/2024	Section 4.6.3: - updated categories and parameter thresholds; - added shift tables from baseline to minimum on-treatment and on-study value.	Yes	Study team's decision: to clarify the definitions and improve the completeness of outputs.
Safety Analysis	11/18/2024	Section 4.6.4: updated the list of variables and categories for the urinalysis analysis.	Yes	Study team's request.

Safety Analysis	11/18/2024	Section 4.6.5: added definitions for “Abnormalities in Vital Signs” and shift tables.	Yes	The definitions were missing.
Safety Analysis	11/18/2024	Section 4.6.6: shift tables added.	Yes	The presentation was missing.
Statistical analysis method for secondary endpoint(s)	11/18/2024	Section 7.1: imputation approach extended to all efficacy parameters.	Yes	Study team's decision: to ensure consistency throughout the methodology for secondary endpoints.
Other	11/18/2024	Throughout the document: minor clarifications, changes, and typographical corrections were made, particularly with regard to the removal of the term 'standard of care' and the addition of 'lipid-lowering' in the ICE definitions for both statin and non-statin therapies.	Yes	To enhance clarity and readability.

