4.6.4.2 Presentations

Treatment emergent urinalysis abnormalities by predefined criteria will be presented in a frequency table. Risk differences between active treatment groups and Placebo will be presented, alongside 95% confidence intervals of the risk difference according to the definitions in Section 4.6.3.1.

Shift tables will present changes from baseline to the maximum (for quantitative parameters) or the worst (for qualitative parameters) on-treatment and on-study values, using the standard categories and classifications described in 4.6.4.1.

Out-of-range values for safety laboratory will be flagged in individual listings as well as summarized descriptively.

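### SAP Table 10 leaves quantitative urine total protein out of the urinalysis analysis, although the protocol collects it at all eight visits as a renal safety biomarker, and SAP Section 2 declares no change

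*SAP*

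**What the plan says.** **Protocol.** The Schedule of Activities (Section 1.2, Table 1) has a row "Urine renal safety biomarkers: albumin, creatinine, total protein", marked at every visit from screening to final follow-up. Table 6 repeats the group under "Urine renal safety biomarkers" and lists total protein there, separately from the dipstick item for protein. Section 8.3.4 says: "The results from the protocol mandated laboratory tests and vital signs will be summarized in the CSR". Section 9.4.3 sets the level of analysis: "Safety data will be summarized descriptively and will not be formally tested".

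**SAP.** Section 4.6.4.1 fixes what is analysed: "The parameters included in the scope of the analysis are specified in the list below". Table 10 then gives seven qualitative items (including protein and erythrocytes) and three quantitative ones: pH, specific gravity and the albumin/creatinine ratio.

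The abnormality rule reads "For quantitative parameters, participants with treatment emergent urinalysis abnormalities will be categorized according to mutually exclusive thresholds", meaning below or above the central-laboratory range. An albumin/creatinine ratio of 300 mg/g or more is an additional criterion. Section 4.6.4.2 continues: "Treatment emergent urinalysis abnormalities by predefined criteria will be presented in a frequency table", with risk differences and 95% confidence intervals against placebo. Shift tables are planned for every Table 10 parameter, to the maximum for quantitative items and to the worst grade for qualitative ones.

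The SAP amendment history says of Section 4.6.4 that it "updated the list of variables and categories for the urinalysis analysis", at the study team's request, and marks this as in line with the protocol. SAP Section 2, which lists changes to protocol-planned analyses, does not mention urine total protein.

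**The concern.** The protocol names three urine measurements as renal safety biomarkers in its schedule. Two of them, albumin and creatinine, reach the SAP as a ratio. The third, total protein, does not reach it at all. Because Table 10 is worded as the scope of the analysis and not as a set of examples, a programmer following the SAP exactly would produce no table for it.

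The albumin/creatinine ratio responds to albumin only, so it does not stand in for total protein. What is at stake is whether a rise in urinary protein that is not mainly albumin would be quantified and set against placebo at each dose, from samples that participants give at every visit. It is also a matter of transparency: the protocol undertakes to summarise mandated tests, and the SAP departs from that without saying so in the section meant for such departures.

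**Working it through.** The plan gives no figure to reproduce on this point. The check is a comparison of passages and one count.

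**Step 1. Trace the protocol's urine renal biomarkers (Table 6) into the SAP.**

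| Protocol item | Where the SAP takes it up |
|---|---|
| Albumin | Table 10, albumin/creatinine ratio |
| Creatinine | Table 10, denominator of that ratio |
| eGFR | Table 9 (blood sample variables) |
| Total protein | Nowhere |

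Two entries look like matches and are not. The total protein in SAP Table 9 is listed under plasma/serum. The protein in Table 10 is in the qualitative column, so it is the dipstick item, which protocol Table 6 lists separately.

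**Step 2. Trace each measure of urinary protein through SAP Sections 4.6.4.1 and 4.6.4.2.**

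| Measure | In Table 10 | Treatment-emergent criterion | Frequency count and risk difference | Shift table by arm |
|---|---|---|---|---|
| Albumin/creatinine ratio | Yes | Below or above range; ≥ 300 mg/g | Yes | Yes, to maximum |
| Dipstick protein | Yes | None stated | No defined entry | Yes, to worst grade |
| Quantitative total protein | No | None | No | No |

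The by-arm column follows from SAP Section 3.3.1 and Table 2: summaries are by treatment group by default, and placebo is marked for safety analyses.

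**Step 3. Check whether the change is declared.** SAP Section 2 lists a safety presentation change (for ECG), so safety outputs are within what that section covers. Urine total protein is not there. The amendment log records that the urinalysis list was updated but not which items moved.

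**Step 4. Count the results affected.** Inputs: 375 randomised participants, about 320 expected to complete 12 weeks (protocol Section 9.2), and eight visits (protocol Table 1). Screening and Day 1 supply baseline, which leaves 8 − 2 = 6 post-baseline visits.

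- Ceiling, no dropout: 375 × 6 = 2,250 results, or 75 × 6 = 450 per arm.
- Completers only, all visits attended: 320 × 6 = 1,920 results.

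These counts give the volume of data left out. They do not measure an effect on any conclusion.

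**The case against.** The other side has several fair points.

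- **Dipstick protein is displayed against placebo.** A reader might infer from the omission that non-albumin proteinuria, or new haematuria, is never compared with placebo. The documents do not support that. Dipstick protein and erythrocytes are both in Table 10 and go into baseline-to-worst shift tables for every arm, placebo included. This point stands in full and limits the concern to the quantitative measure.
- **Other renal routes exist.** Falls in eGFR and rises in creatinine have graded criteria with risk differences (SAP Sections 4.6.3.1 and 4.6.3.2), and the albumin/creatinine ratio has two criteria. Clinically relevant laboratory deterioration is reportable as an adverse event (protocol Section 8.3.4) and tabulated by arm. All of this stands, but none of it summarises urine total protein.
- **The protocol asks only for descriptive safety summaries.** It therefore does not require a risk difference for dipstick items, and their absence from the frequency table is no protocol breach. That stands. It does not excuse total protein, which gets no summary of any kind.
- **Section 4.6.4.2 says that out-of-range laboratory values are flagged and summarised.** This could be stretched to cover total protein. The sentence sits in a section whose scope Table 10 has closed, and it names neither the parameter nor a comparison. The reading is possible but weak.
- **No renal risk is listed in the protocol's risk assessment (Table 2).** True, and it keeps the stakes modest. The protocol nevertheless chose to collect the measure at every visit.

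**Conclusion.** The concern holds as a conflict between protocol and SAP over one parameter. Quantitative urine total protein is scheduled at all eight visits, its summary is promised by protocol Section 8.3.4, and the SAP's closed list omits it without declaring a change. As a result, non-albumin proteinuria appears in the laboratory outputs only as a dipstick shift table, with no quantitative summary, frequency count or risk difference. The data left out are at most 2,250 post-baseline results before dropout. Counting all eight visits would give 375 × 8 = 3,000, but that includes the two baseline samples.

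The conclusion rests on reading the scope sentence in Section 4.6.4.1 as exhaustive, which is its plain sense, and on no other planned output covering the parameter. No primary or secondary endpoint is touched, and nothing in the documents suggests that a signal is expected.

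A reader might also infer that the November 2024 SAP amendment removed total protein. The log does not show which items changed, so that cannot be concluded. What can be said is that the current list is marked as in line with the protocol and, on this item, is not.

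**What to change.** Add urine total protein, normalised to the urine creatinine already collected, to the quantitative column of SAP Table 10. Apply the rules that column already has: abnormality by central-laboratory range where one is available, entry in the frequency and risk-difference table, and a shift table to the maximum value. Neither document gives a reference range for such a ratio. If the laboratory supplies none, the SAP should say so and give a descriptive summary by arm and visit instead. If the sponsor prefers to leave the parameter out, Section 2 should record the omission with its reason. That would make the departure visible but would leave the data unsummarised.

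Optional and secondary: before unblinding, state which dipstick grade change counts as treatment-emergent for protein and erythrocytes, or state that these two items are shown in shift tables only. Where to put the threshold is open to debate, and the documents do not settle it.

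The cost is SAP text and a few table rows. No new samples, assays or visits are needed.

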4.6.4.2 Presentations

Treatment emergent urinalysis abnormalities by predefined criteria will be presented in a frequency table. Risk differences between active treatment groups and Placebo will be presented, alongside 95% confidence intervals of the risk difference according to the definitions in Section 4.6.3.1.

Shift tables will present changes from baseline to the maximum (for quantitative parameters) or the worst (for qualitative parameters) on-treatment and on-study values, using the standard categories and classifications described in 4.6.4.1.

Out-of-range values for safety laboratory will be flagged in individual listings as well as summarized descriptively.

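### Urine albumin/creatinine ratio is summarised only through cut-offs, with no by-visit value or change from baseline, so a modest dose-related rise in albuminuria could be missed

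*SAP*

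**What the plan says.** The Schedule of Activities (Protocol 1.2) has a row for "Urine renal safety biomarkers: albumin, creatinine, total protein", marked at screening, Days 1, 8, 15, 29, 57 and 85, and the Day 99 follow-up.

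SAP 4.6.4.1, Table 10, places the albumin/creatinine ratio in the quantitative column. The same section then defines the ways it is used:

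- A quantitative urine result counts as abnormal when it lies below the central laboratory's LLN or above its ULN.
- This ratio has one further cut: "In addition, abnormalities in 'albumin/creatinine' (ratio) will be defined as ≥ 300 mg/g".
- Shift categories are below LLN, within range and above ULN.

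SAP 4.6.4.2 lists the outputs. The main one is tabular: "Treatment emergent urinalysis abnormalities by predefined criteria will be presented in a frequency table". The same counts are to be contrasted with placebo, arm by arm, as differences in proportions with 95% intervals. There is also a shift table from baseline to the maximum value, and out-of-range results are flagged in listings and summarised.

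For blood samples, SAP 4.6.3.2 says "All parameters will be presented as continuous variables with descriptive statistics for all visits at which an assessment is scheduled", and adds change from baseline. SAP 4.6.5.2 (vital signs) and 4.6.6.2 (ECG) likewise plan visit-level descriptive statistics and change from baseline.

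**The concern.** UACR is a continuous measurement taken repeatedly in every participant, yet each planned table reduces it to which side of a limit it falls on. A participant who moves from 6 to 12 mg/g contributes nothing to a count above an upper limit of, say, 30 mg/g. One who moves from 28 to 32 counts in full. If most participants start well below the limit, which is plausible but not stated in the documents, most of the information in the samples goes unused.

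The treatment of urine is also out of line with the rest of the SAP. The other three groups of quantitative safety data are shown on their measured scale, and nothing explains why UACR is not.

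At stake is the ability to see a modest, dose-related rise in albuminuria. Protocol 9.2 says the sample size is driven by safety and tolerability, and Protocol 2.1 says the data will guide the choice of doses. A table showing no excess of urine abnormalities could be read as more reassuring than it is.

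**Working it through.** **1. Is a full-scale UACR summary scheduled anywhere?**

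| Place | What it covers | Schedules a UACR summary? |
|---|---|---|
| SAP 3.3.1 | Which statistics a continuous summary contains | No |
| SAP 4.6.3.2 | By-visit values for haematology and chemistry; Table 9 does not list UACR | No |
| SAP 4.6.4.2 | Frequency table, risk differences, shift table, out-of-range flags | No |
| Protocol 8.3.4 and 9.4.3 | Laboratory results to be summarised and tabulated in general terms | Not specifically |

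**2. Inputs.** The plan gives no UACR figure to reproduce. From the documents: 375 / 5 = 75 randomised per arm; at 15% discontinuation, 375 × 0.85 / 5 = 63.75, matching the stated 64. The interval is the SAP's own (4.6.3.1): difference ± 1.96 × SE, with unpooled variances.

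Assumed, not in the documents: log-normal UACR, median 6–10 mg/g, between-person log-SD (σb) 0.8–1.0, visit-to-visit log-SD (σw) 0.5–0.7, ULN 30 mg/g, five on-treatment visits, one dose versus placebo, and a constant r-fold rise from the first of those visits.

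**3. Full scale: log change from baseline at Week 12.** The SD of the change is √2·σw, SE = √2·σw·√(2/n), and power ≈ Φ(ln r / SE − 1.96). With n = 75:

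- r = 1.5 (ln r = 0.405), σw = 0.5: SE = 0.1155, z = 3.51, power Φ(1.55) = 94%.
- r = 1.5, σw = 0.7: SE = 0.1617, z = 2.51, power Φ(0.55) = 71%.
- r = 1.25 (ln r = 0.223): z = 1.93 and 1.38, power 49% and 28%.

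**4. Cut above ULN.** A treatment-emergent case has baseline ≤ 30 and at least one of five values > 30. With m = ln(median) + σb·x and x standard normal, its probability is the average over x of Φ((ln 30 − m)/σw) × [1 − Φ((ln 30 − m − ln r)/σw)⁵]. For r = 1.5 and n = 75, the two ends of the range are:

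- Median 6, σb = 1.0, σw = 0.7: 16.1% on placebo and 27.5% on active. SE = √[(0.161 × 0.839 + 0.275 × 0.725)/75] = 0.067, z = 1.72, power about 40% (41% by simulation).
- Median 10, σb = 0.8, σw = 0.5: 17.2% and 33.1%. SE = 0.070, z = 2.28, power about 63% (63% by simulation).

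**5. Cut at 300 mg/g.** In the most favourable case (median 10, σb = 1.0, σw = 0.7) the probabilities are about 0.9% and 2.3%. That is 75 × 0.009 = 0.7 against 75 × 0.023 = 1.7 participants. Simulated power there is 5–6%, and close to zero elsewhere.

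**6. Results, 75 per arm** (cut columns by simulation; last column by the formula in step 3):

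| True rise | Above ULN | ≥ 300 mg/g | Log change at Week 12 |
|---|---|---|---|
| 1.25-fold | about 16–24% | at most about 2% | 28–49% |
| 1.5-fold | about 41–63% | at most about 6% | 71–94% |
| 2-fold | about 84–98% | at most about 23% | 99–100% |

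With 64 per arm and a 1.5-fold rise, the ULN cut gives 36–56%. The step 3 formula gives SE 0.125 and 0.175, z = 3.24 and 2.32, and so 90% and 64%.

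**The case against.** Several arguments on the other side have force.

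- **Safety is descriptive.** Protocol 9.4.3 says safety data will not be formally tested, so power is a borrowed yardstick. That stands: the percentages only illustrate lost sensitivity. But the plan already gives placebo risk differences with 95% intervals for urine, so an estimate with a nominal interval is the same kind of output.
- **The inputs are assumed.** This stands. The ULN is held at 30 mg/g, and the laboratory's range is not given. A quantification floor would also blunt the full scale: with an illustrative floor of 5–8 mg/g, a baseline-adjusted Week 12 analysis of a 1.5-fold rise falls from 77–97% to about 59–95%. The gain shrinks but remains.
- **Pooling helps.** The SAP also compares AZD0780 Total with placebo. If every dose produced the 1.5-fold rise, the pooled ULN comparison would reach about 63–86%, against 93–100% on the full scale. Pooling helps less if only the higher doses have the effect.
- **Renal function is covered.** Serum creatinine and eGFR are in Table 9, with by-visit values, change from baseline and thresholds relative to baseline. The protocol's risk table names no renal risk. This limits the consequence.

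A reader might infer that a rise within the normal range would appear in no planned urine output, or that renal safety goes unmonitored. The documents do not support either. A general upward shift pushes some participants over the ULN (17% to 33% in the second example of step 4), individual out-of-range values are flagged, and creatinine and eGFR are shown in full. A reader might also infer that a repeated-measures model is needed. The SAP gives no safety variable such a model, not even QTcF or blood pressure, and an unadjusted change from baseline already captures most of the gain.

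**Conclusion.** The gap is real and limited. SAP 4.6.4.2 reports UACR only through cut-offs and a categorical shift, and no other section schedules a summary on the measured scale. Rises of about 1.25- to 1.5-fold could be missed. For a 1.5-fold rise, the chance of an interval excluding no effect is roughly 41–63% with the better cut and 71–94% with a simple log change. Rises of about 2-fold would mostly be seen at the ULN cut. These figures depend on the assumed UACR distribution, ULN and visit-to-visit variation; the direction does not depend on any single one of the values tried. No figure in the documents is wrong, and no trial conclusion turns on this. It is a cheap improvement.

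**What to change.** Add to SAP 4.6.4.2, before unblinding:

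> UACR will be summarised by treatment group and scheduled visit as observed value (geometric mean, geometric CV, median, Q1, Q3) and ratio to baseline. The geometric mean ratio of each dose, and of AZD0780 Total, to placebo will be given with a nominal 95% CI at Week 12.

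Keep the existing frequency and shift tables. A repeated-measures model for log UACR, and a similar summary of the urine total protein/creatinine ratio, are optional.

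The cost is one extra table from data already collected, with no new samples, visits or participants. The downside is a few more nominal safety comparisons to interpret.
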